8.1.6 Visit dates

For each visit, the date recorded by the Investigator in the eCRF (variable SVSTDTC in the SDTM SV dataset) will be considered as the visit date in all the algorithms and the listings.

8.1.7 Data re-allocation

The following general rules to handle repeated assessments will be considered:

- PFT (spirometry):
 - If the spirometry was repeated before the first study medication intake, the last assessment performed will be considered as the Visit 1 assessment in all the analyses.
 - If the spirometry was repeated at a visit after the first study medication intake, the assessment performed ‘post-bronchodilator’ will be considered as the visit assessment in all the analyses.
- 12-lead ECG:
 - in case of multiple measurements associated to the same timepoint (e.g. triplicate ECGs), the average value will be considered for HR, RR interval, PR interval, QRS duration, QT interval, QTcB interval and QTcF interval.
 - The last 12-lead ECG performed before the first study medication intake will be considered in the analysis as the Visit 1 ECG.
- Vital signs, physical examination, clinical laboratory tests:
 - The last assessment performed before the first study medication intake of each parameter will be considered in the analysis as the Visit 1 assessment.

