- 7 There will be sparse PK sampling in all subjects to be taken on any 2 of the 3 dosing occasions (Days 1, 3, or 5): one sample to be taken pre-dose, one sample taken 0-2 h post-dose, one sample taken 4-8 hours post-dose, and one sample no earlier than 12 hours post-dose. ECG will be taken at approximately the same time as with PK sample. ECGs should be taken before the PK sample.

- 8 Spirometry will be taken 'on bronchodilator' and ideally in the morning. For an individual spirometry should be taken at approximately the same time of day (during the acute phase \pm 1 hour and in the stabilisation phase \pm 2 hour window). Ideally this will be taken at least 1 hour after regular long acting bronchodilators and 30 minutes after short acting bronchodilator medication. Time of last short and long acting bronchodilators will be documented.
- 9 Spirometry at Screening should be performed 'on bronchodilator'. This will be taken after any regular long acting bronchodilator administration and 30 minutes after short acting bronchodilator medication.
- 10 Perform BMI and 6MWT at Day 14. BODE will then be calculated.
- 11 Please refer to the Laboratory Manual for clarification of whether the biomarker is to be analysed in either serum or plasma.
- 12 If the subject is discharged before Day 7, they will return to the hospital daily for assessment.
- 13 If screening and Day 1 occur on different days spirometry will be repeated on day 1 before dosing with study treatment and result obtained on day 1 may be used as baseline.
- 14 If historical spirometry data within last 12 months does not include pre and post SABA value this should be obtained during the stabilisation phase, for demographic purposes.
- 15 Physical examination at screening should include a minimum of chest, cardiovascular and abdominal examination. At all other time points a minimum of chest auscultation is required. Additional examination is at the discretion of the Investigator as indicated by the subjects' clinical condition.
- 16 A gynaecological history should be taken (from females only) with subjects specifically asked about vaginal bleeding, discharge or pain. Any new vaginal bleeding (other than normal menstruation), vaginal discharge or pain after dosing should be investigated by vaginal examination and any required specialist assessment.
- 17 Document in eCRF which symptoms of the acute exacerbation are present out of increased sputum, increased cough and increased dyspnoea.

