3. CRQ
4. Collect data for the exploratory composite scale
5. Physical examination, including vital signs (body temperature, RR, pulse rate, blood oxygen [measured using a pulse oximeter], systolic and diastolic blood pressure) and weight
6. Urine and serum (Week 26 only) pregnancy test, women of childbearing potential only
7. Blood sample for clinical laboratory tests (haematology [INR and prothrombin time not required], biochemistry, and inflammatory blood biomarkers) to be taken at least 6 hours after SABA (whenever possible; times of sample collection and SABA intake must be recorded), after 8 hours of fasting (wherever possible), and after completion of ECG and vital signs (body temperature, RR, pulse rate, systolic and diastolic blood pressure)
8. Urinalysis (specific gravity, pH, protein, glucose, blood)
9. If sputum or bronchoalveolar culture is collected for any medical reason (qualitative or quantitative culture), the result should be recorded in the eCRF
10. 'On bronchodilator' spirometry. This will ideally be performed in the morning, at least 1 hour after regular long acting bronchodilator administration and 30 minutes after short acting bronchodilator medication
11. Collect mMRC dyspnoea scale
12. COPD exacerbation reporting (EXACT-PRO) completed by the subject in the evening
13. Pre and post bronchodilator spirometry (week 8, 12 or 26). Where this is not available from historical spirometry this will be collected during the stabilisation period, for demographic purposes.

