11.2.1 Spirometry

Pulmonary function tests will be carried out under medical supervision in either a clinic or hospital and will be recorded using a computer-operated spirometer.

Lung function measurements and daily calibration of the spirometer will be done to the recommendations of the official Statement of the European Respiratory Society (ERS) and the American Thoracic Society (ATS). All sites will be provided with equipment and a central spirometry laboratory will be used. Investigator sites will be trained to the use of the system during the investigator meeting. All calibration reports should be printed and kept with the source study documents.

The specific procedures for the central spirometry will be provided to the investigator by the central spirometry company.

Forced Expiratory Volume in the 1st second in litres (FEV₁, L) and Forced Vital Capacity (FVC, L) will be recorded daily from Days 1 to 7 and on Days 10 and 14 during Part 1 of the study and at all visits of the Part 2 of the study. At either Week 8, 12, and 26 pre and post bronchodilator spirometry will be performed, for demographic purposes, if this information is not available from historical spirometry. This is additional to the 'on bronchodilator' spirometry, with the 'on bronchodilator' measurement being the priority.

The chosen value should not exceed the next by more than 150 mL. If the difference is larger, up to 8 measurements will be made and the highest value reported. The ratio FEV₁/FVC will be derived from this highest value of each parameter.

Predicted values will be automatically calculated with the demographics data recorded in the centralised system.

If more than one spirometry has been conducted within the 12 months before the study the most recent result, outside the exacerbation, will be used as the pre study value.

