- 7 There will be sparse PK sampling in all subjects to be taken on any 2 of the 3 dosing occasions (Days 1, 3, or 5): one sample to be taken pre-dose, one sample taken 0-2 h post-dose, one sample taken 4-8 hours post-dose, and one sample no earlier than 12 hours post-dose. ECG will be taken at approximately the same time as with PK sample. ECGs should be taken before the PK sample.

A Symbol of Excellence

Statistical Analysis Plan (SAP)

- 8 Spirometry will be taken 'on bronchodilator' and ideally in the morning. For an individual spirometry should be taken at approximately the same time of day (during the acute phase \pm 1 hour and in the stabilisation phase \pm 2 hour window). Ideally this will be taken at least 1 hour after regular long acting bronchodilators and 30 minutes after short acting bronchodilator medication. Time of last short and long acting bronchodilators will be documented.
- 9 Spirometry at Screening should be performed 'on bronchodilator'. This will be taken after any regular long acting bronchodilator administration and 30 minutes after short acting bronchodilator medication.
- 10 Perform BMI and 6MWT at Day 14. BODE will then be calculated.
- 11 Please refer to the Laboratory Manual for clarification of whether the biomarker is to be analysed in either serum or plasma.
- 12 If the subject is discharged before Day 7, they will return to the hospital daily for assessment.
- 13 If screening and Day 1 occur on different days spirometry will be repeated on day 1 before dosing with study treatment and result obtained on day 1 may be used as baseline.
- 14 If historical spirometry data within last 12 months does not include pre and post SABA value this should be obtained during the stabilisation phase, for demographic purposes.
- 15 Physical examination at screening should include a minimum of chest, cardiovascular and abdominal examination. At all other time points a minimum of chest auscultation is required. Additional examination is at the discretion of the Investigator as indicated by the subjects' clinical condition.
- 16 A gynaecological history should be taken (from females only) with subjects specifically asked about vaginal bleeding, discharge or pain. Any new vaginal bleeding (other than normal menstruation), vaginal discharge or pain after dosing should be investigated by vaginal examination and any required specialist assessment.

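### SAP 8.1.7 does not exempt the Week 8, 12 or 26 pre/post-bronchodilator test from its repeat-spirometry rule, so it can displace the 'on bronchodilator' value to which the protocol gives priority

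*SAP*

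**What the plan says.** SAP 8.1.7 (Data re-allocation) has two rules for repeated spirometry. The second begins "If the spirometry was repeated at a visit after the first study medication intake". It states that the assessment labelled 'post-bronchodilator' "will be considered as the visit assessment in all the analyses". It makes no exception for study phase, visit or the reason for the extra test.

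The protocol creates a planned situation in which a late visit has more than one spirometry record:

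- Protocol 11.2.1 says that in the Stabilisation Phase "pre and post bronchodilator spirometry will be performed, for demographic purposes, if this information is not available from historical spirometry". It describes this as extra to the usual spirometry, with the 'on bronchodilator' "measurement being the priority".
- Protocol 9.1.3.3, item 13, lists "Pre and post bronchodilator spirometry (week 8, 12 or 26" among the follow-up procedures, which implies one of the three visits.
- Footnote 14 of the protocol's schedule of assessments gives the trigger: "If historical spirometry data within last 12 months does not include pre and post SABA value". The SAP's copy of that footnote (section 3.3) repeats the purpose: "this should be obtained during the stabilisation phase, for demographic purposes".

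SAP section 9, which lists departures from the protocol, does not mention any change to which spirometry value counts.

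**The concern.** At a late visit where the extra test is done, a patient has three records: 'on', 'pre' and 'post'. The protocol treats the first as the efficacy measurement and the other two as background description. The SAP rule, as worded, picks the third.

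Two sets of secondary analyses use late spirometry:

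- **Normalisation** of FEV1 and FEV1/FVC at Weeks 8, 12 and 26 (SAP 8.6.3.2).
- **Time to improvement** of 100 mL and of 80 mL, whose reporting periods run to Weeks 13-26 (SAP 8.6.3.3).

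In these, some patients would contribute a 'post' value and others an 'on' value at the same nominal visit, and which one would depend on how complete the patient's old lung-function record was. The absolute late rates could shift for a reason unrelated to recovery. A record choice that the protocol settles would be reopened at programming.

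**Working it through.** The plan gives no figure on this point, so the check is mainly a comparison of texts, followed by a labelled illustration.

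**Step 1. Which record does the rule select?**

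| Record at the late visit | Protocol status | SAP 8.1.7, literal reading | SAP 8.1.7, loose reading |
|---|---|---|---|
| 'on bronchodilator' | priority | not selected | eligible |
| 'pre' | demographic | not selected | not eligible |
| 'post' | demographic | selected | eligible |

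The loose reading arises because the SAP also uses 'post-bronchodilator' for the ordinary Visit 1 test (8.4.6) and for the baseline severity factor (8.6.1). Section 8.6.2.3 says that patients enrolled under V4.0 and V5.0 had all spirometry done 'on bronchodilator'. Neither reading gives the protocol's answer.

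**Step 2. Which outputs are exposed?**

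- The primary MMRM uses Days 2 to 7 (SAP 8.6.2.1): not exposed.
- FEV1 and FVC comparisons at Days 3 to 14 and the FEV1 AUCs end by Day 14 (8.6.3.1, 8.6.3.4): not exposed.
- Normalisation at Weeks 8, 12 and 26: exposed. The reference is the pre-study value (7.1.4.2, 7.1.4.3).
- Time to +100 and +80 mL: exposed only in patients who had not met the threshold at an earlier visit. The reference is Baseline (7.1.4.4).

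**Step 3. How large could it be?** The documents give no 'post' minus 'on' difference. Assumptions, for illustration only:

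- The ratio of 'on' FEV1 to pre-study FEV1 at the visit is Normal with mean 1.00 and SD 0.15.
- The 'post' test raises the mean ratio by g and leaves the SD unchanged.

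Share normalised = Φ((1.00 + g − 0.89) / 0.15)

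- g = 0: Φ(0.11/0.15) = Φ(0.733) = 0.768
- g = 0.02: Φ(0.13/0.15) = Φ(0.867) = 0.807
- g = 0.05: Φ(0.16/0.15) = Φ(1.067) = 0.857
- g = 0.10: Φ(0.21/0.15) = Φ(1.400) = 0.919

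These shares apply to affected patients at the affected visit. Across a whole arm the shift is diluted. If 30% of patients had the test (assumed), spread evenly over three visits, 10% would be affected at each. The arm's rate would move by 0.10 × (85.7 − 76.8) = 0.9 points at g = 0.05, or 0.10 × (91.9 − 76.8) = 1.5 points at g = 0.10.

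For time to improvement, at an assumed FEV1 of 1.2 L, a 5-10% gain is 1,200 × 0.05 = 60 mL to 1,200 × 0.10 = 120 mL, the same order as the 80 and 100 mL thresholds. No calculation was made for FEV1/FVC, since FVC can rise along with FEV1.

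**The case against.** The best defence is terminological. Since the SAP calls the ordinary bronchodilated test 'post-bronchodilator', the rule may only mean that a pre-bronchodilator value should not be used. It can also be argued that an additional demographic test is not a repeat, so the rule is never triggered. Both readings are possible, and it is not shown that the authors intended a substitution. But the SAP states neither, and under the first reading 'on' and 'post' both qualify with nothing to separate them.

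The gain is also likely to be smaller than a usual reversibility response. The comparison is 'post' with 'on', and 'on' tests are ideally done at least 1 hour after a long-acting and 30 minutes after a short-acting bronchodilator (schedule footnote 8). That stands, and it is why the illustration starts at zero.

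A reader might infer more than the documents support:

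- **That late normalisation is inflated.** This is not established. The comparator is the pre-study value, not Baseline. SAP 8.4.3 summarises pre-study results both pre- and post-bronchodilator, and the SAP does not say which is the reference. If it is a post-bronchodilator value, the 'post' test could be the closer match.
- **That the treatment comparison is biased.** Selection depends on the content of pre-randomisation records in a blinded trial. Bias between arms would need chance imbalance or a bronchodilator response that differs by arm.
- **That the rule is right for V2.0/V3.0 patients and wrong for V4.0/V5.0 patients.** The earlier protocol texts are not available, only a log of changes. A patient enrolled before an amendment may have late visits after it.

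**Conclusion.** The point holds as a conflict between SAP 8.1.7 and Protocol 11.2.1 that should be settled before unblinding. The rule either selects the wrong record or fails to select one, normally at one late visit per selected patient. The expected harm is mixed measurement within arms and possibly shifted absolute late rates in secondary endpoints, within a study whose analyses are all declared exploratory (Protocol 13.5.1).

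The size is unknown. The movement from 77% to between 77% and 92% in affected patients rests entirely on the assumed Normal(1.00, 0.15) ratio and the assumed 0-10% gain. The number of affected patients is not given either.

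**What to change.** Amend the second spirometry bullet of SAP 8.1.7 to say that:

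1. At any post-dose visit with an 'on bronchodilator' assessment, that assessment is the visit value in all efficacy analyses.
2. The Week 8, 12 or 26 pre/post pair is used for demographic summaries only.
3. The existing 'post-bronchodilator' rule applies only at visits with no 'on bronchodilator' assessment, such as visits done under earlier protocol versions.

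Define the rule by the test performed at the visit, not by the protocol version at enrolment, so that patients whose late visits followed an amendment are handled correctly.

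The cost is a short rewording of one bullet and a record-selection flag in the analysis dataset. It needs no new data and changes neither the sample size nor the primary analysis.

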8.1.8 Exclusion of data from the statistical analysis

Spirometries assessed as being of unacceptable quality will be removed upstream from the clinical database, thus excluded from the statistical analysis.

8.1.9 Data listings

All the relevant subject data, including those derived, will be presented in individual subject data listings. All listings will be sorted by treatment regimen, investigational site, patient number, date/time and visit. The patient’s sex and age will be stated on each listing. Unless otherwise stated, data listings will be based on all patients randomised.

Unscheduled visit results will be included in date/time chronological order within patient listings, but will not be tabulated.

8.2 Subject disposition

All patients who provided informed consent will be included in a summary of patient accountability. The number of subjects screened, the number of screen failures, the frequency of patients randomised (by treatment regimen and overall), the frequency and percentage of patients in the Safety population, in the ITT population, in the PP population and in the PK population (by treatment regimen and overall) will be summarised.

Subject disposition information will be summarised by treatment regimen and overall. The number

of subjects completing and withdrawing study drug intake, completing Acute Exacerbation Phase, completing and withdrawing from the study will be tabulated in the study disposition table which will also include the reasons for treatment discontinuation and early withdrawal of the patient as reported on the eCRF. The summary will also be presented by country.

Finally, the reasons for screen failure as reported on the eCRF will be tabulated.

The follow-up time (number of days from first study treatment to last contact) will be summarised descriptively.

A listing will include the randomisation/kit numbers, randomisation date/time and study disposition data (on all subjects screened).

8.3 Protocol deviations

The number of patients excluded from ITT, Safety, PP and PK populations and reasons for exclusion will be summarised by treatment regimen and overall.

Population membership details will be listed, including reason for exclusion from each population (on randomised patients).

All protocol deviations identified will be summarised by treatment regimen and overall.

All protocol deviations identified will be listed based on data recorded on the eCRF and/or protocol deviation Logs (from CTMS).

8.4 Demographics and baseline characteristics

Statistical comparisons will be performed whenever possible in order to examine the relationship between each demographics and baseline characteristic and treatment regimen. The associated two-sided p-values representing the comparison across the treatment regimens [one-way ANOVA test, Kruskal-Wallis test (or Wilcoxon Rank-Sum test for pairwise treatment regimens), Pearson's Chi-square test or Fisher's exact test, as appropriate] will be reported in the summary tables and regarded as descriptive.

See Appendix F for SAS code used to implement these standard univariate tests.

For the final analysis, if the Safety and ITT populations are equal, the tables on the ITT population will not be presented if available also on the Safety population.

8.4.1 Demographics

Demographic variables will be listed and summarised by treatment regimen and overall. This will include age, sex, race, country of origin, weight, height and BMI. Separate summaries will be produced using the Safety, ITT and PP populations.

8.4.2 Smoking status

Smoking status at Screening (ex-smoker or current smoker), duration of smoking (years) and

number of pack-years will be presented by treatment regimen and overall. Separate summaries will be produced using the ITT and PP populations.

8.4.3 COPD history

Duration of COPD disease (years), current (last year) severity of the disease, number of moderate or severe COPD exacerbations in the last 12 months before screening [as a continuous and categorical variable (0, 1, 2, 3, >3)], time since last documented COPD exacerbation (months), treatment with systemic corticosteroids or antibiotics (or both) or hospitalisation for the last documented COPD exacerbation, pre-study spirometry results (pre- and post-bronchodilator) from most recent PFT performed outside an exacerbation in the last 12 months will be presented by treatment regimen and overall. Separate summaries will be produced using the ITT and PP populations.

8.4.4 Baseline treatment for COPD

COPD treatment category at study entry (Monotherapy: Long-Acting β 2-Agonist [LABA] alone, Long-Acting Muscarinic Antagonist [LAMA] alone, Inhaled Corticosteroids [ICS]; Dual therapy: LABA+LAMA, LABA+ICS, LAMA+ICS; Triple therapy: LABA+LAMA+ICS; Other) will be presented by treatment regimen and overall. Separate summaries will be produced using the ITT and PP populations.

8.4.5 Current COPD exacerbation data

Duration of current COPD exacerbation symptoms (days) and worsening of respiratory symptoms (breathlessness, wheeze, cough, reduction in exercise tolerance, fever, change in sputum production [change in quantity; aspect purulent vs. non purulent], unusual increase of use of “rescue” medication, other worsened symptoms) will be presented by treatment regimen and overall. Separate summaries will be produced using the ITT and PP populations.

Other exacerbation characteristics data not tabulated above will be listed.

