7 INTRODUCTION

7.1 Background

Chronic obstructive pulmonary disease (COPD) is a progressive condition that is a major cause of poor health and death worldwide ([GOLD Guidelines 2015](#)) and contributes significantly to health care costs and comorbidity ([Lopez et al 2006](#)), ([Chapman et al 2006](#)). COPD is a chronic disease for which worldwide prevalence (currently estimated at 210 million) and mortality rate (2.74 million died in 2000) are still increasing. COPD is currently ranked as the fourth cause of death ([GOLD Guidelines 2015](#)) and is anticipated to become the third by 2020.

COPD exacerbations account for 50-75% of the cost of healthcare services in COPD ([Mittmann et al 2008](#), [Toy et al 2010](#)). The impact of the exacerbations on patient's overall well-being is significant, and the symptoms and deterioration in lung function may persist for several weeks before recovering to Baseline values ([Seemungal et al 2000](#)). On average, COPD patients experience approximately 1-3 exacerbations per year, although this varies with the severity of underlying COPD ([Seemungal et al 2009](#); [Langsetmo et al 2008](#)). A median duration of exacerbation of 13 (6 to 24) days has been reported in patients receiving SoC, and 9 (6 to 14) days in patients receiving long-term therapy with macrolide antibiotics in addition to SoC. Of these exacerbations, 37% (patients treated with long-term macrolides in addition to SoC) and 60% (patients treated with SoC) had not resolved within 10 days ([Seemungal et al 2008](#)). A recent retrospective observational database study showed a median duration of hospital stay due to moderate to severe COPD exacerbation of 9 to 10 days ([Molinari et al 2015](#)). Based on published literature, approximately 32% of exacerbations occur within 8 weeks of a preceding exacerbation event ([Hurst 2009](#)), and approximately 60% of patients are readmitted to the hospital within 12 months because of an exacerbation ([Almagro et al 2006](#); [Garcia-Aymerich et al 2003](#); [Lau 2001](#)), highlighting the need for more effective treatments.

Since frequent COPD exacerbations are known to promote disease progression ([Donaldson 2002 et al](#); [Rennard and Farmer 2004](#)), there is a high unmet need for more effective treatment to reduce the number and severity of exacerbations as well as the length and number of hospitalisations.

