9.3 Selection of Study Population

9.3.1 Inclusion criteria

1. Male and female adults aged ≥ 40 years
2. Written informed consent obtained prior to any study-related procedure
3. Presence of an active exacerbation of the ongoing COPD requiring hospitalisation for treatment:

*“A sustained worsening of the patient’s condition (dyspnoea, cough and/or sputum production/purulence), from the stable state and beyond normal day-to-day variations, that is acute in onset and necessitates a change in regular medication in a patient with underlying COPD that includes prescriptions of systemic corticosteroids and/or antibiotics **and** need for hospitalisation”.*

4. Subjects with a diagnosis of COPD with spirometry performed outside an exacerbation within the last 12 months prior to the Screening Visit
5. Current smokers or ex-smokers with a smoking history of at least 10 pack years (pack-years = [number of cigarettes per day x number of years/20])
6. A FEV1 < 65% of the predicted normal value
7. A **documented** history of at least one moderate or severe COPD exacerbation in the 12 months preceding the Screening Visit that required antibiotics and/or systemic corticosteroid (addition or increment on subject current use) as defined below:
 - *“A sustained worsening of the patient’s condition (dyspnoea, cough and/or sputum production/purulence), from the stable state and beyond normal day-to-day variations, that is acute in onset and necessitates a change in regular medication in a patient with underlying COPD that includes prescriptions of systemic corticosteroids and/or antibiotics **or** need for hospitalisation”*
 - Also, documented visits to an emergency department due to COPD exacerbation are considered acceptable to fulfil this criterion.
8. Current regular treatment for COPD (categories C and D according to GOLD guidelines, updated 2015) for at least 2 months prior to the Screening Visit with either:
 - Inhaled corticosteroids/long-acting β_2 -agonist combination, long-acting muscarinic antagonist without regular use of any short-acting bronchodilator (any short-acting bronchodilator allowed if used as needed [PRN]) or
 - Inhaled corticosteroids/long-acting β_2 -agonist combination, without regular use of any short-acting bronchodilator (any short-acting bronchodilator allowed if used PRN or

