13.5.6 Analysis of Further Endpoints

Demographic data and subjects' characteristics at Screening will be listed and summarised using descriptive statistics. Formal statistical analysis will not be performed on Baseline demographic data.

Medical history will be coded using MedDRA. An incidence table by body system and preferred term will be presented by treatment regimen.

Compliance with study medication will be summarised descriptively by treatment regimen.

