7.1.3 Definitions relative to demographic and other baseline characteristics

7.1.3.1 Age

Age at informed consent will be calculated as:

Age (years) = (date of informed consent - date of birth + 1) / 365.25

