7.1.3.6 Current COPD exacerbation duration

- Duration of current COPD exacerbation symptoms will be calculated in days as:
(date when symptoms stopped – date when symptoms started + 1)
- Time until complete recovery from the current COPD exacerbation will be calculated in days as:
(date when patient achieved complete recovery from the current exacerbation – date when symptoms started).

Where ‘Date when symptoms started’, ‘Date when symptoms stopped’, and ‘Date when patient achieved complete recovery from the current exacerbation’ are recorded on the ‘Current COPD Exacerbation’ form of the eCRF.

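### The SAP tabulates and tests the duration of index exacerbation symptoms as a baseline characteristic, although it depends on a stop date that normally falls after dosing

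*SAP*

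**What the plan says.** SAP 8.4.5 lists for tabulation by regimen "Duration of current COPD exacerbation symptoms (days) and worsening of respiratory symptoms". SAP 7.1.3.6 gives the formula: "date when symptoms stopped – date when symptoms started + 1". That definition sits under the SAP 7.1.3 heading "Definitions relative to demographic and other baseline characteristics". The same section derives a time until complete recovery from the index episode.

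The opening of SAP 8.4 governs all its subsections: "Statistical comparisons will be performed whenever possible in order to examine the relationship between each demographics and baseline characteristic and treatment regimen". The two-sided p-values, from one-way ANOVA, Kruskal-Wallis or Wilcoxon, chi-square or Fisher tests as appropriate, "will be reported in the summary tables and regarded as descriptive".

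On entry, protocol 9.3.1 requires "Presence of an active exacerbation of the ongoing COPD requiring hospitalisation for treatment". On baseline testing, protocol 13.5.6 states: "Formal statistical analysis will not be performed on Baseline demographic data". SAP Section 9, which lists departures from the protocol, does not mention the added baseline tests.

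**The concern.** A baseline characteristic should be fixed before the first dose. This one is completed only when symptoms end. If BCT197 shortened symptoms, the difference would be shown in the baseline tables, where a reader takes a small p-value as chance imbalance or a fault in randomisation.

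The figure would also be selective. Without a stop date there is no duration, so patients who die, withdraw or never resolve can drop out. SAP 7.2.2.2 imputes only a missing day and leaves missing months and years as they are. The SAP gives censoring rules for its time-to-event variables (Tables 2-1 to 6), but none for this one.

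**Working it through.** **1. Is it a post-dosing variable?** Setting the sections side by side:
- Entry requires an active exacerbation (protocol 9.3.1), with standard-of-care treatment begun less than 24 hours before randomisation and dosing (protocol 9.1.1). Symptoms ending before the first dose would be unusual.
- SAP 7.1.4.10 starts the clock for time to next exacerbation at the date index symptoms stopped, so it treats that date as falling within follow-up.
- SAP 7.1.4.16 and 8.6.4.3 sum steroid dose from symptom start to symptom stop and analyse it as an exploratory endpoint.
- For later exacerbations, SAP 8.6.3.11 summarises symptom duration and time to complete recovery in the efficacy section.
- SAP 8.4.6 to 8.4.9 restrict their variables to Screening or Visit 1 (pre-dose for the scores). SAP 8.4.5 has no such limit and no exemption from the 8.4 tests.

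Only the index episode has its symptom duration filed as baseline.

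**2. The plan's own figure.** The 85 per arm used below comes from SAP Section 5: difference 100 mL, SD 230 mL, two-sided alpha 0.05, power 80%. The normal approximation gives 84 per arm. The t-test solution is 84.01, which rounds up to 85. The figure reproduces and nothing in this point changes it.

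**3. How visible might a benefit be? (illustration only)** Protocol 7.1 reports: "A median duration of exacerbation of 13 (6 to 24) days has been reported in patients receiving SoC, and 9 (6 to 14) days", the second figure being for added long-term macrolide. It does not say what the ranges are. Reading 6 to 24 as quartiles of a lognormal:
- log-SD = ln(24/6) / (2 × 0.6745) = 1.3863 / 1.349 = 1.028
- P(longer than 10 days) = Φ(ln(13/10) / 1.028) = Φ(0.255) = 0.60, matching the 60% unresolved at 10 days that protocol 7.1 gives for standard of care
- Two-arm comparison of log durations, 13 versus 9 days: expected z = ln(13/9) / (1.028 × √(2/85)) = 0.3677 / 0.1577 = 2.33, which corresponds to p = 0.020

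SAP 8.4 tests across all three arms, so the closer check is a simulation: 85 per arm, placebo median 13 days, both active arms sharing one median, durations rounded up to whole days. It used 4,000 trials per row at log-SD 1.03 and 2,000 at the other two values. Entries are the share of trials with p below 0.05, Kruskal-Wallis / ANOVA.

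| Active median (days) | log-SD 1.03 | log-SD 0.8 | log-SD 0.6 |
|---|---|---|---|
| 13 (no effect) | 5.4% / 4.9% | not run | not run |
| 11 | 18% / 13% | 26% / 20% | 42% / 38% |
| 10 | 37% / 26% | 56% / 46% | 84% / 79% |
| 9 | 64% / 46% | 85% / 76% | 98% / 97% |
| 8 | 87% / 69% | not run | not run |

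**4. Limits of the illustration.** With the same log-SD, a 9-day median implies 1 − Φ(ln(10/9) / 1.028) = 46% unresolved at 10 days, against the 37% that protocol 7.1 quotes with macrolide. The quoted 9 (6 to 14) implies a smaller log-SD, ln(14/6) / 1.349 = 0.63. The contrast comes from macrolide therapy and is not a forecast for BCT197. All 85 per arm are assumed to have a stop date.

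**The case against.** The strongest reply is that little depends on this variable.
- The p-values are labelled descriptive, and protocol 13.5.1 calls all analyses exploratory.
- Index symptom duration is not a protocol endpoint.
- Recovery is analysed as efficacy elsewhere: EXACT-PRO improvement and sustained recovery (SAP 8.6.3.7 and 8.6.3.8), readiness for discharge (8.6.3.14), time to FEV1 improvement (8.6.3.3) and spirometry normalisation (8.6.3.2).
- SAP 8.4.5 says exacerbation data that are not tabulated will be listed, so time to complete recovery is not lost.

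All of this stands, and it rules out several stronger readings:
- A reader might infer that faster recovery would never be estimated as a treatment effect. That is true only of the investigator-recorded symptom duration and time to complete recovery of the index episode.
- A reader might fear that adjustment for the apparent imbalance would remove the effect. No planned model contains duration. The models in SAP 8.6.1 and 8.6.2.1 use time from symptom start to first dose, which is known before dosing.
- A reader might take protocol 13.5.6 to bar every p-value in SAP 8.4. The sentence names demographic data only.
- A reader might take p = 0.02 as what the table would show. It is the two-arm p-value at the expected z under one assumed effect and spread.

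None of this makes a variable that depends on a post-dosing date a baseline characteristic. SAP 7.1.3.7 also derives a time from symptom stop to first dose, which might suggest that stopping before dosing was envisaged. The entry criterion makes that the exception.

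**Conclusion.** The point holds in a limited form. Followed as written, the SAP would print a post-randomisation outcome in a baseline table with a between-arm p-value, computed only in patients with a stop date. If treatment shortened symptoms, a significant baseline difference could follow: in roughly 46% to 64% of trials for 13 versus 9 days at log-SD 1.03, fewer for smaller effects and more if durations vary less. These rates rest on the lognormal form, the quartile reading and complete stop dates, none of which the documents confirm. The classification error itself rests on no numerical assumption.

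The harm is to interpretation of the baseline tables and to the reporting of one recovery measure. The sample size, alpha, primary FEV1 estimate and protocol-listed secondary analyses do not change.

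A separate and smaller matter: testing demographic variables under SAP 8.4 conflicts with protocol 13.5.6 and is missing from SAP Section 9.

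**What to change.** - In SAP 8.4.5 keep only what is known before dosing: symptoms at entry and time from symptom start to first dose. Remove symptom duration from the baseline tables and from the 8.4 tests, and move its definition out of SAP 7.1.3.
- Report duration as a post-baseline exploratory outcome, preferably as time from first dose to symptom stop by Kaplan-Meier, with unresolved patients censored at last contact. Censoring at the date of death would treat those who died as still able to recover. Either keep deaths as not recovered to the end of follow-up, or use cumulative incidence with death as a competing event.
- Time to complete recovery of the index episode may be reported in the same way. This is optional, since it is not a protocol endpoint.
- Remove the p-values on demographic variables from SAP 8.4, or list the change in SAP Section 9.

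The cost is SAP wording and one table, two if time to complete recovery is added. The symptom and recovery dates are already on the Current COPD Exacerbation form.
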